5.4 DATA AND SAFETY MONITORING PLAN

5.4.1 Principal Investigator/Research Team

The clinical research team will meet on a routine basis when patients are being actively treated on the trial to discuss each patient. Decisions about ongoing enrollment and intervention will be made based on the toxicity data from prior patients.

All data will be collected in a timely manner and reviewed by the principal investigator or a lead associate investigator. Adverse events will be reported as required above. Any safety concerns, new information that might affect either the ethical and or scientific conduct of the trial, or protocol deviations/reportable events will be immediately reported to the IRB using iRIS.

The principal investigator will review adverse event and response data on each patient to ensure safety and data accuracy. The principal investigator will personally conduct or supervise the investigation and provide appropriate delegation of responsibilities to other members of the research staff.

5.4.2 Monitoring Plan

Accrual and safety data will be monitored by the principal investigator, who will provide oversight to the conduct of this study. The PI will continuously evaluate implementation of the protocol for any unusual or unpredicted complications that occur and will review the data for accuracy and completeness.

Abbreviated Title: RFA + TACE with RO Beads

Version Date: 04/13/2018

6.0 QUALITY ASSURANCE

The NIH Clinical Center's quality assurance program will conduct study monitoring at least annually or more frequently as required. Patient consent documents, primary outcome and safety laboratory results and diagnostic test results will be monitored for accuracy, correct dating, and agreement between case report forms and source documents. All regulatory reports, reviews and amendments, adverse events, problem reports related to study, the investigator credentials, training records, and the delegation of responsibility log will be reviewed during monitoring visits. Any major findings will be summarized in writing and reported to the study pi who will be responsible for submitting the monitoring report to the IRB.

7.0 STATISTICAL CONSIDERATIONS

This is a proof of concept/feasibility study with a small number of evaluable patients and data points. Data collected will not be sufficient to provide meaningful statistical analysis.

Sample size was derived from historical experience with pilot feasibility observational studies, where a population of 20-30 evaluable patients should provide initial information to begin to characterize the imaging features of the approach, which is the main goal. This should allow for adequate slight variations in dosages and anatomy to inform such a pilot study. The precise characterization of the imaging features will require a much larger future study, but this pilot study outcomes and imaging features could be used to power future studies, depending upon the primary aims. No statistical analysis is required to power this trial, as it is a pilot feasibility study, and the outcomes related to imaging features will not be statistically analyzed, other than simple descriptive statistics. Descriptive statistics will be provided in summary tables.

- Categorical variables will be summarised using frequency distribution: number of observations (N) and percentages (%).
- Continuous variables will be summarized using standard quantitative statistics:
 - number of observations (N),
 - mean, standard deviation (STD),
 - median and
 - range (minimum and maximum observed values).

When relevant, the 95% confidence intervals (CI) will also be displayed.

For instance, qualitative analyses may be done to compare virtual and actual perfusion characteristics (such as overlap) of LUMI beads using CBCT before, during, and after LUMI beads injection.

If fewer than 20 evaluable patients are enrolled, then the variety of imaging features seen may be limited. Using fewer than 20 evaluable patients could start to substantially compromise the ability of the study to provide the necessary rationale for further work in refining and developing the clinical use of this approach. Since the emphasis is that this is a PILOT study, this recommended study size of N=20 EVALUABLE patients seem to be a good compromise.

Lastly, assuming that possibly up to 33% of recruited patients may turn out to either be ineligible or that their data will be inevaluable, a total of N=30 patients will need to be recruited to ensure having (roughly) 20 evaluable patients. If a patient's follow-up imaging is not available but their procedural data is adequate they will be considered evaluable. Inevaluable patients are defined

Abbreviated Title: RFA + TACE with RO Beads

Version Date: 04/13/2018

as patients whose data cannot be reliably recorded in terms that satisfy the primary endpoint. This could occur if the data cannot be graded in terms of visibility due to technical issues such as patient motion or small doses of beads used in a small volume of tissue.

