4.1.2 On Study Data Collection

We will also document bead visibility data during embolization. This information will be collected using a qualitative particle visibility scale by applying a 3-point scale: 0, definitely not visible; 1, probably visible; and 2, definitely visible [21].

Intra-procedural, post treatment, and follow up images will all be saved and stored in PACS. Patient images will be anonymized prior to transfer to a secure work station for analysis. CRF's and non-image data will be stored in the DRD shared drive which has limited access. The DRD shared drive is backed up and managed by the NIH DCRI in keeping with the protection and confidentiality guideline of the Privacy Act of 1974.

Any grade 3 events and higher occurring up to 72 hours post treatment (either with combined RFA and TAE or with TAE alone) will be collected and recorded in the study database as adverse events, except those listed in the Exclusions to Adverse Event Data Collection section (see Section 4.1.3). Grade 2 events will be collected and recorded if not resolved before the patient is considered off treatment (72 hours post treatment). Grade 1 events will not be collected or reported.

Abbreviated Title: RFA + TACE with RO Beads

Version Date: 04/13/2018

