4.3 RESPONSE CRITERIA

4.3.1 Definitions

- Evaluable for bead visibility: All patient imaging will be evaluated for the visibility of the LC LUMI beads using a 3 point scale: 0, definitely not visible; 1, probably visible; and 2, definitely visible as defined the treating interventional radiologists. Other characteristics may be noted such as the radiopacity of the beads, visibility of the beads in the tumor, overall location of beads in relation to the tumor or targeted site.
- Evaluable for toxicity: All patients will be evaluable for toxicity from the time of their treatment with LC LUMI radiopaque beads up to 72 hours post completion of treatment. Grade 3 or greater adverse events, including allergic reactions, collected during this time period, will be followed until resolution. Expected or anticipated adverse events from the research or the study device will not be collected. See Section **4.1.3** for details.
- Evaluable for imaging characteristics: Only those patients who are eligible for the study, have received at least one treatment of TAE, and have had their disease re-evaluated per standard of care imaging will be considered evaluable.

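### Section 7.0 can drop a treated patient whose beads could not be graded because little was given; Section 4.3.1 has no 'not gradable' level, and the two sections disagree on missing follow-up imaging

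*Combined protocol and SAP*

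**What the plan says.** Section 7.0 sets a target of 20 evaluable patients from 30 recruited. It calls a patient inevaluable when the data cannot be recorded reliably enough for the primary endpoint. Its example is a record that "cannot be graded in terms of visibility due to technical issues such as patient motion or small doses of beads used in a small volume".

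Section 4.3.1, under the entry for bead visibility, says: "All patient imaging will be evaluated for the visibility of the LC LUMI beads using a 3 point scale: 0, definitely not visible". The other levels are 1 (probably visible) and 2 (definitely visible), and the treating interventional radiologists do the scoring. There is no level for an image that cannot be graded, and the entry does not say whether the unit is the patient, lesion, session or image.

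A separate entry in Section 4.3.1, for imaging characteristics, admits only eligible patients who "have received at least one treatment of TAE, and have had their disease re-evaluated per standard of care imaging will be considered evaluable". Section 7.0 instead says that if a patient's "follow-up imaging is not available but their procedural data is adequate they will be considered evaluable".

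Section 4.1.2 adds: "We will also document bead visibility data during embolization". On reporting, Section 7.0 says: "Categorical variables will be summarised using frequency distribution: number of observations (N) and percentages". It does not say which patients or images form the base of those percentages.

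**The concern.** The two example reasons for inevaluability differ in kind. Motion spoils an image however visible the beads would have been. A small amount of radiopaque material in a small volume is a plausible cause of poor visibility. Setting such patients aside can therefore remove some of the least favourable cases. Section 7.0 also says the sample should take in slight variation in dose and anatomy, so these cases belong to what the pilot is meant to describe.

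Without a 'not gradable' level or a working rule for grade 0, two readers could treat the same faint image differently. One scores 0 and counts the patient; the other calls it ungradable, and the patient may drop out. Both would be following the protocol.

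What is at stake is how the visibility percentages are read. N would show how many were counted, but not why others are absent. Section 7.0 says the pilot's outcomes and imaging features could be used to power later studies, so a later planner could take a gradable-only figure for the rate in all patients given beads.

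**Working it through.** **The plan's own figure.** Section 7.0 gives 20 evaluable patients ("this recommended study size of N=20 EVALUABLE patients seem to be a good compromise") and an allowance ("assuming that possibly up to 33% of recruited patients may turn out to either be ineligible or that their data will be inevaluable"). 20 / (1 − 0.33) = 29.85, rounded up to 30. The total reproduces and is not in dispute. The allowance pools ineligible with inevaluable patients, so it does not say how many treated patients might be ungradable.

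**The rules side by side.**

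| Patient | 4.3.1, bead visibility | 4.3.1, imaging characteristics | 7.0 |
|---|---|---|---|
| Treated, images too faint to grade, small bead load | Imaging is to be scored 0–2; no other level | Evaluable if eligible and re-imaged | May be inevaluable |
| Treated, adequate procedural images, no follow-up imaging | Procedural images are scored | Not evaluable | Evaluable |

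The second row is a direct conflict between the last two columns, reading disease re-evaluation as follow-up imaging. Because visibility is recorded during embolization, such a patient can have a score. The conflict exists whether or not any low-dose case occurs.

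**Illustration of size.** The documents give no visibility counts. Assume one result per patient, scores 1–2 counted as visible, n = 20 graded, g graded visible, and k treated but not gradable.

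- Graded-only rate: p = g/n.
- All-treated rate: between g/(n+k), if no ungradable patient had visible beads, and (g+k)/(n+k), if all did.
- Width of that range: k/(n+k).
- Largest overstatement by p: p·k/(n+k). Largest understatement: (1−p)·k/(n+k).

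With g = 18, p = 90%:

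| k | Lowest | Highest | Width (points) | Max. over | Max. under |
|---|---|---|---|---|---|
| 0 | 90% | 90% | 0 | 0 | 0 |
| 1 | 18/21 = 86% | 19/21 = 90% | 4.8 | 4.3 | 0.5 |
| 3 | 18/23 = 78% | 21/23 = 91% | 13.0 | 11.7 | 1.3 |
| 5 | 18/25 = 72% | 23/25 = 92% | 20.0 | 18.0 | 2.0 |

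With g = 14 (70%) and k = 3, the range is 14/23 = 61% to 17/23 = 74%; p is at most 9.1 points too high or 3.9 too low. If the ungradable patients had the same true rate as the graded ones, the error would be zero.

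**Against sampling error.** The exact (Clopper-Pearson) 95% interval for 18/20 is 68.3% to 98.8%, so its lower limit is 90 − 68.3 = 21.7 points below the estimate. Every shift in the table is smaller than that. The interval allows only for chance among the graded patients, however, and not for who was left out.

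**The case against.** The strongest reply has four parts.

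- **A visibility set exists.** Section 4.3.1 has an entry for bead visibility that covers all patient imaging, while the Section 7.0 rule sits in the paragraph justifying N=30 and is never tied to the summary tables. This stands in part. A reader might infer that the plan has no visibility set; it has one, based on images. What is missing is the unit and any statement of how the Section 7.0 exclusion acts on it.
- **Grade 0 and ungradable differ in words.** Grade 0 is a confident negative; ungradable means a technical failure. That is fair as language, but no code or working rule carries the distinction into the data.
- **The bias is conjecture.** A reader might infer that low dose alone excludes patients, or that the percentages must be too high. The text supports neither. Grading must also fail, and it is the patient, not one image, who becomes inevaluable. Visibility is recorded during embolization, and Section 3.2.3 adds a CT within 2 months, so a patient ungradable on one image may be gradable on another. An ungradable case is unknown, not shown to be invisible.
- **The study is descriptive.** Section 7.0 limits reporting to simple descriptive statistics, and the objective in Section 1.1.1 is imaging characteristics with a qualitative perfusion comparison. This stands, and it sets the severity.

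A reader might also use the whole 33% allowance to contrast 20/20 = 100% with 20/30 = 67%. That counts ineligible patients as treated and ungradable and then scores all of them as not visible. The documents support neither step.

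**Conclusion.** The point holds as a minor one, limited to the descriptive visibility result. Section 7.0 permits a treated patient to be set aside for a reason plausibly linked to the outcome. Section 4.3.1 gives no place to record such a case, and the two sections give opposite answers for a patient without follow-up imaging.

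The consequence for the percentages is conditional: it arises only if they are based on the Section 7.0 evaluable set, which is a natural reading but not an explicit one. They could then overstate visibility among all patients given beads. Neither size nor direction can be derived from the documents, and k may be 0. The figures above rest on assumed counts, one result per patient and scores 1–2 taken as visible. On those assumptions, 18/20 graded visible with k = 3 leaves the all-treated rate between 78% and 91%. No hypothesis test, stopping rule or go/no-go decision uses the figure.

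**What to change.** In Sections 4.3.1 and 7.0:

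1. Keep every patient who received beads in the visibility table and state the unit (patient, lesion or image). Do not use small dose or small volume to remove a patient from it.
2. Show grades 0, 1 and 2, plus a 'not gradable' row split by reason: small dose or volume, motion, missing image. Score 0 only when the images are adequate and the beads are not seen; do not force ungradable cases to 0.
3. Report the graded-only percentage g/n beside the all-treated range g/(n+k) to (g+k)/(n+k). Do not give g/(n+k) as the single rate: it is the lower bound, and it understates visibility if some ungradable beads were in fact visible.
4. Reconcile the two evaluability rules so that a patient with adequate procedural images but no follow-up imaging stays in the visibility summary.

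The cost is wording in two sections and a slightly larger table. No extra patients, readers or images are needed, and N=30 is unaffected. The downside is that reported visibility may look less favourable: in the k = 3 illustration, a range reaching down to 78% would stand beside the 90%.

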8 COLLABORATIVE AGREEMENTS

8.1 CRADA

The investigational study device is provided by another party under a Collaborative Agreement [Cooperative Research and Development Agreement (CRADA) with BTG/Biocompatibles UK Limited (#08-02412)].

9 HUMAN SUBJECTS PROTECTIONS

9.1 RATIONALE FOR SUBJECT SELECTION

This study intends to enroll 30 participants who have primary or metastatic liver cancer. The study seeks to enroll both women and men who meet eligibility criteria including whites, non-whites and minorities. Patients who may be unable to comprehend the study requirements and associated risks may not be able to be enrolled. The intent of this study is a proof of concept safety and feasibility study and as such, children would not be the appropriate patient population.

9.1.1 Selection Based On Gender, Ethnic, Race

Subjects from both genders and all racial/ethnic groups are eligible for this study if they meet the eligibility criteria. Efforts will be made to extend accrual to a representative population.

Statistical analysis to explore ethnic, race and gender differences will not be performed, as this study is not powered to explore any such differences.

9.1.2 Justification for Exclusion

Patients that are pregnant will be excluded from this trial because of concern that ionizing radiation may be harmful to the developing fetus. Patients with altered mental status that prevents consent or answering questions will be excluded. Patients with uncorrectable coagulopathies may be at increased risk for bleeding, and will be excluded. Patients with multiple co-morbidities, sepsis, or multiple high-risk medical problems may be at increased risk for morbidities or mortalities, and will be excluded. This does not change standard transarterial embolization exclusions.

9.2 PROTECTION OF PATIENT RIGHTS

The Radiology and Imaging Sciences Department is responsible for protecting all subjects involved in human experimentation. This is accomplished through the IRB mechanism and the process of informed consent. The IRB reviews all proposed studies involving human experimentation and ensures that the patient's rights and welfare are protected and that the potential benefits and/or the importance of the knowledge to be gained outweigh the risks to the individual. The IRB also reviews the Informed Consent document associated with each study in order to ensure that the consent document accurately and clearly communicates the nature of the research to be done and its associated risks and benefits. The IRB must give full board approval of the protocol and consent documents before the study may begin at a site.

9.2.1 Confidentiality

The Radiology and Imaging Sciences Department is responsible for the confidentiality of the data associated with patients registered/randomized in this study in the same manner it is

Abbreviated Title: RFA + TACE with RO Beads

Version Date: 04/13/2018

responsible for the confidentiality of any patient data within its sphere of responsibility. For patients registered/randomized to this study, there are additional considerations related to the necessity of sharing of research data with the ACOSOG-CC and representatives of NCI and OHRP.

9.3 PARTICIPATION OF CHILDREN

Children will not be eligible for this study.

9.4 PARTICIPATION OF SUBJECTS UNABLE TO GIVE CONSENT

Adults unable to give consent are excluded from enrolling in the protocol. However, re-consent may be necessary and there is a possibility, though unlikely, that subjects could become decisionally impaired. In these cases, the subject will be taken off study.

9.5 EVALUATION OF BENEFITS AND RISKS/DISCOMFORTS AND RISKS/BENEFITS ANALYSIS

The risks inherent to this device itself should be identical to the risks of undergoing the clinically indicated procedure, and are outlined in detail below. This use of beads for embolization has been standard therapy for liver tumors for decades. The LUMI bead is very similar in composition to the widely used over the last decade and commercially available LC bead™. The LUMI LC bead is basically an LC bead with attached iodine to make it visible on x-rays, like regular iodine contrast. The risks of these LUMI LC beads are discussed in the table below:

No	Potential Hazard	Resultant Harm	Risk Evaluation Discussion	Mitigation Strategy
1	Transarterial embolization Thermal ablation	
• Pain• Bleeding• Infection• Nausea• Anesthesia complications• Pneumothorax• Liver abscess formation• Acute cholecystitis• Gastric ulceration• Pancreatitis• Misembolization• Radiation Injury• Allergic reactions to anesthesia medications• Allergic reaction to intravenous contrast• Liver failure• Stomach ulcer• Postembolization syndrome (24-72 hours following chemoembolization, during hospital	The LC beads will be placed using standard of care transarterial embolization protocol. The tumor site is accessed via an inguinal artery	Pre-operative clearance from the anesthesia service. Pain and Palliative care consult as clinically indicated Evaluation of any outstanding cardiology, pulmonology or other co-morbid disease states before IR procedures; routine general sedation and peri-operative, antiemetics, antacids, antibiotics, local anesthesia and post operative patient controlled analgesia, bedrest, nursing surveillance and antibiotics. Patients with known contrast allergies will be pretreated per standard of care Patient with known allergies to any anesthesia agents will receive comparable anesthesia medications that they can tolerate Peri-procedure imaging to evaluate immediate LC bead placement enhanced by the beads radiopaque element will allow immediate visualization

No	Potential Hazard	Resultant Harm	Risk Evaluation Discussion	Mitigation Strategy
		
observation period)
 
 • Abdominal visceral injury (from non-target embolization, 1-2 weeks following embolization): 		
of misembolization.
 
Patient are admitted to the inpatient hospital ward during the immediate post-operative period and monitored.
 
Post-operative changes in patient comfort vital signs or diagnostics such as liver enzymes will prompt further evaluation.

2	LC Lumi beads	Allergic Response	The preclinical experience does not raise concerns that the radiopaque LC beads produces any known acute allergic response (see Investigator's Brochure).	Patient with known allergy to LC beads or its components will be excluded from the study
3	LC Lumi beads	Endotoxin adverse reaction	The preclinical experience does not raise concerns that the radiopaque LC beads produces any known acute endotoxin response (see Investigator's Brochure).	
Labeled non-pyrogenic Endotoxin testing in animal models proved no change in temperature during an observation period following injection of extracted LC bead LUMI.
 
Acutely febrile patients will be excluded from the procedure as is standard of care

4	LC Bead LUMITM Bead	Genotoxicity, Carcinogenicity, reproductive toxicity	The preclinical experience does not raise concerns that the radiopaque LC beads produces any known genotoxicity, carcinogenotoxic or reproductive toxic adverse events (see Appendix C, Section 0)	Patients who are of reproductive age will be counseled on use of adequate birth control. All women who are of reproductive age and are not sterile or post-menopausal will be tested for pregnancy prior to all imaging.
5	LC Bead LUMITM beads	Systemic or local toxicity	The preclinical experience does not raise concerns that the radiopaque LC beads produces any known acute systemic or local adverse response (see Appendix C, Section 0)	Patient are admitted to the inpatient hospital ward during the immediate post-operative period and monitored. Post-operative changes in patient comfort, physical exam, vital signs or diagnostics such as liver enzymes will prompt further evaluation with imaging and immediate treatment.

Abbreviated Title: RFA + TACE with RO Beads

Version Date: 04/13/2018

